11.4.2 Physical examination

A thorough physical examination of the subject including whole body inspection of the skin, auscultation of heart, lungs, and abdomen, palpation of the abdominal organs, and basic neurological status must be performed according to the schedule of trial procedures (Section 4). Presence of foot dermatitis will be documented. The investigator should perform the same examinations as in clinical practice as a minimum.

If the screening physical examination results in a finding, which is abnormal and of clinical significance, it will be at the investigator's discretion to decide if the subject should be randomised into the trial (respecting exclusion criterion no. 20).

Reporting in eCRF

It will be recorded in the eCRF if a physical examination was performed and the investigator's evaluation ('normal', 'abnormal, not clinically significant', 'abnormal, clinically significant'); if a physical examination was not performed, a reason must be given.

Clinically significant abnormal findings at screening will be documented as medical history in the eCRF. At subsequent visits, any clinically significant deterioration of a pre-existing condition as well as any new clinically significant sign, symptom, or illness will be reported as an AE in accordance with Section 13.3.

11.4.3 ECG

A single 12-lead resting digital ECG will be recorded after the subject has been supine for at least 5 minutes at the visits indicated in the schedule of trial procedures (Section 4).

A preliminary evaluation of the ECGs will be performed by the investigators to evaluate immediate subject safety. As a minimum, the date of ECG collection will be recorded in the source documents.

The ECG data will be transferred to a central ECG service company for central evaluation. A cardiologist at the ECG service company will analyse and interpret the ECG data. The ECG service company will provide ECG evaluation reports to the trial sites.

The investigator must evaluate all abnormal ECG results ('clinically significant' or 'not clinically significant') and sign and date. The investigator has the final decision on the clinical significance of ECG abnormalities.

If the screening ECG results in a finding, which is abnormal and of clinical significance, it will be at the investigator's discretion to decide if the subject should be randomised into the trial (respecting exclusion criterion no. 20).

The collection and transmission of ECG data will be described in a separate ECG manual. Test dummy transmissions will be undertaken prior to trial conduct to ensure that transmissions can be made, and that date and time settings are correctly set.

Reporting in eCRF

It will be recorded in the eCRF if an ECG was performed and the investigator's assessment of ECG results ('normal', 'abnormal, not clinically significant', 'abnormal, clinically significant'); if an ECG was not performed, a reason must be given.

Clinically significant abnormal findings at screening will be documented as medical history in the eCRF. At subsequent visits, any clinically significant deterioration of a pre-existing condition as well as any new clinically significant sign, symptom, or illness will be reported as an AE in accordance with Section 13.3.

11.4.4 Laboratory testing

Blood and urine samples will be collected according to the schedule of trial procedures (Section 4). See [Panel 13](#) for an overview of the individual clinical laboratory parameters to be assessed in this trial.

Central laboratory

Chemistry, haematology, urinalysis (if applicable), serology, and serum pregnancy tests will be analysed by a central laboratory, which will provide results to the trial sites. The investigator must evaluate all results outside the reference range ('clinically significant' or 'not clinically significant') and sign and date. The signed and dated version will be filed with the investigator's trial documentation. Clinically significant abnormal tests must be repeated to confirm the abnormality.

If a screening laboratory result is abnormal and of clinical significance, it will be at the investigator's discretion to decide if the subject should be randomised into the trial (respecting exclusion criteria no. 16, 20, 21, 22, and 30).

A laboratory manual will be provided to the trial sites specifying the procedures for collection, processing, storage, and shipment of samples, as well as laboratory contact information specific to this trial.

Tests performed at the trial site

Urine samples will be tested at the trial site with a dipstick; if abnormal, a urine sample will be sent to the central laboratory for further analysis.

Women of childbearing potential will have urine pregnancy tests performed at the trial site at the visits indicated in the schedule of trial procedures in Section 4.

Panel 13: Clinical laboratory tests

Chemistry	Haematology	
Sodium	Erythrocytes	
Potassium	Haematocrit	
Creatinine	Haemoglobin	
Urea nitrogen	Erythrocyte mean corpuscular volume	
Calcium	Erythrocyte mean corpuscular haemoglobin concentration	
Alkaline phosphatase	Leukocytes	
Aspartate aminotransferase	Neutrophils, neutrophils/total cells	
Alanine aminotransferase	Lymphocytes, lymphocytes/total cells	
Gamma glutamyl transferase	Monocytes, monocytes/total cells	
Bilirubin ¹	Eosinophils, eosinophils/total cells	
Lactate dehydrogenase	Basophils, basophils/total cells	
Cholesterol	Thrombocytes	
LDL cholesterol	Serology²	
HDL cholesterol	Hepatitis B virus surface antigen	
Triglycerides	Hepatitis B virus surface antibody	
Glucose (non-fasting)	Hepatitis B virus core antibody	
Albumin	Hepatitis C virus antibody	
Protein	HIV-1 antibody	
	HIV-2 antibody	
	Immunoglobulin E	
	Tuberculosis test^{2,3}	
	Interferon gamma release test	
Urinalysis ⁴	Serum pregnancy test ^{2,5}	
Protein	Choriogonadotropin beta	
Glucose		
Ketones		
Occult blood		
Leukocytes		
Nitrite		

- 1) If bilirubin is above ULN, direct and indirect bilirubin will also be measured.
- 2) Measured at screening only.
- 3) Subjects with high risk of latent tuberculosis (e.g. prior residence in or travel to countries with high prevalence of tuberculosis, close contact with a person with active tuberculosis, or a history of active or latent tuberculosis where an adequate course of treatment cannot be confirmed) must be tested.
- 4) Urine samples will be tested at the trial site (dipstick). In case of abnormal dipstick results, a urine sample will be sent to the central laboratory for microscopic examination (leukocytes, erythrocytes, and casts).
- 5) Only women of childbearing potential. In addition, urine pregnancy tests will be performed at the trial site.

Abbreviations: HDL, high density lipoprotein; HIV, human immunodeficiency virus; LDL, low density lipoprotein.

Reporting in eCRF

The site staff will record in the eCRF if a sample was taken and the investigator's assessment of the results ('normal', 'abnormal, not clinically significant', 'abnormal, clinically significant').

The date and the outcome of the urine pregnancy test will be recorded in the eCRF ('positive', 'negative').

Clinically significant abnormal laboratory results at screening will be documented as medical history in the eCRF. At subsequent visits, any clinically significant deterioration of a pre-existing condition as well as any new clinically significant sign, symptom, or illness will be reported as an AE in accordance with Section 13.3.

11.4.5 Subject assessment of local tolerability

Subjects will provide an assessment of local tolerability according to the schedule of trial procedures (Section 4).

The subject will retrospectively be asked by the investigator to assess stinging/burning in connection with the IMP applications since their last visit. The highest (worst) skin reaction score across treatment area(s) will be recorded in the eCRF by use of the 4-point scale shown in [Panel 14](#).

Panel 14: Subject assessment of local tolerability after IMP application

Grade	Stinging/burning
0 (none)	No stinging or burning
1 (mild)	Slight warm, tingling sensation, not really bothersome
2 (moderate)	Definitive warm, tingling sensation, that is somewhat bothersome
3 (severe)	Hot, tingling/stinging sensation that has caused definite discomfort.

Subject assessment of local tolerability will be performed after safety assessments by the investigator ([Panel 6](#)). Local tolerability reactions are not reported as AEs; however, if they qualify as an SAE, they will be reported as described in Section 13.4.1.

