10.1 General principles

A subject may withdraw from the trial (i.e., withdraw from treatment and protocol-defined interventions) or permanently discontinue trial treatment (i.e., stop treatment only, but agree to continued protocol-defined interventions) at any time (prior to first dose or during the treatment period) if the subject, the investigator, or LEO considers that it is not in the subject's best interest to continue.

If a subject withdraws from the trial, he/she may request destruction of any samples taken and not tested, and the investigator must document this in the subject's source documentation.

Subjects who withdraw from the trial and subjects who discontinue trial treatment will not be replaced.

Data to be recorded in the eCRF

The primary reasons for withdrawal from the trial, discontinuation of IMP, and not attending the primary endpoint visit at Week 16, if applicable, must be recorded in the medical records and on the end of trial form in the eCRF where the following options are available:

- Lack of efficacy
- Adverse event
- Withdrawal by subject
- Lost to follow-up
- Pregnancy
- Death
- Other

If 'adverse event' or 'other' is selected, a specification must be provided in the eCRF with a clear link to the specific AE if applicable.

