10.2 IMP discontinuation rules

10.2.1 Reasons for discontinuation of IMP

Subjects will discontinue IMP in the event of:

- An AE that, in the opinion of the investigator or sponsor's medical expert, contraindicates further dosing.

- Evidence of pregnancy.
- Initiation of rescue medication.
- Clinically important laboratory abnormalities:
 - Alanine aminotransferase and/or aspartate aminotransferase values $>3\times\text{ULN}$ with total bilirubin $>2\times\text{ULN}$ (unless elevated bilirubin is related to Gilbert Meulengracht Syndrome).
 - Confirmed aspartate aminotransferase and/or alanine aminotransferase $>5\times\text{ULN}$ (for more than 2 weeks).

It is not allowed to re-start IMP treatment after discontinuation of IMP.

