13.3 Reporting of adverse events

AEs reported by the subject or observed by the investigator must be recorded on the AE form of the eCRF and should be described in the following manner:

The *AE term* must be in precise English medical terminology (that is, not necessarily the exact words used by the subject). Whenever possible, a specific diagnosis should be stated (for example 'allergic contact dermatitis').

For cutaneous AEs the *location* must be part of the AE description and may be described as e.g., the face, scalp, back, chest, arm, leg, trunk, or limb. Additionally, the location should be described using the following terminology:

- Lesional/perilesional (≤ 2 cm from the border of lesion(s) treated with IMP).
- Distant (> 2 cm from the lesion border).

The *duration* of the AE must be reported by the start date and stop date of the event (it will also be recorded if the event is ongoing). In addition, it will be recorded if the AE started prior to start of IMP.

AEs must be classified in terms of severity, causality and outcome according to the definitions in [Appendix 2](#).

Action taken with IMP: any action taken with IMP as a consequence of the AE must be recorded (dose not changed, drug withdrawn, not applicable, unknown).

Other action taken: any other action taken as a result of the AE must be recorded (none, concomitant medication, concurrent procedure).

Withdrawn from trial due to this AE: it must be recorded whether the AE led to withdrawal from the trial.

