14.3 Statistical analysis

14.3.1 Disposition of subjects

The reasons for permanent discontinuation of IMP and withdrawal from trial will be presented for all randomised subjects by treatment group.

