14.3.9.1 Adverse events

AEs will be coded during the course of the trial according to Medical Dictionary for Regulatory Activities (MedDRA). AEs will be presented by preferred terms and primary system organ class (SOC).

Treatment-emergent AEs will be summarised; however, all AEs recorded during the course of the trial will be included in subject data listings. An event will be considered treatment-emergent if started after the first use of IMP or if started before the first use of IMP and worsened in severity after first dose of IMP. The tabulations described in the following will only include the treatment-emergent events. In each of the tabulations, AEs are defined by MedDRA preferred terms within primary SOC.

An overall summary of the number of events and the number (percentage) of subjects with any treatment-emergent AEs, deaths, SAEs, premature discontinuations from the trial due to AEs, treatment-related AEs and severe AEs will be presented.

The number of AEs and number of subjects with each type of AEs will be tabulated by treatment group.

The severity for each type of AE will be tabulated by treatment group. Where there are several recordings of severity for a given type of AE, severity will be taken as the most severe recording for that AE.

The causal relationship to IMP for each type of AE will be tabulated by treatment group. Where there are several recordings of causal relationship to the IMP for a given type of AE, causal relationship will be taken as the most-related recording from the last report of that AE, since that is when the investigator will be in possession of most information and so best able to judge causal relationship.

Related AEs are defined as AEs for which the investigator has not described the causal relationship to IMP as 'not related'. The number of subjects with each type of related AE will be tabulated.

SAEs will be evaluated separately and a narrative for each will be given.

Adverse events of special interest will be tabulated by treatment group.

AEs leading to withdrawal from trial and AEs leading to permanent discontinuation of IMP will be tabulated by treatment group.

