Appendix 1: Definitions of adverse events and serious adverse events

Adverse event definition

An AE is defined as any untoward medical occurrence in a patient or clinical investigation subject administered a pharmaceutical product and which does not necessarily have a causal relationship with this treatment. An AE can therefore be any unfavourable and unintended sign (including an abnormal laboratory finding), symptom, or disease temporally associated with the use of a medicinal (investigational) product, whether or not related to the medicinal (investigational) product. (ICH Harmonized Tripartite Guideline for Good Clinical Practice, E6 (R1)).

This definition includes:

- Accidental injuries.
- Events related to trial procedures.
- Reasons for any unfavourable and unplanned change in medication (drug and/or dose).
- Clinically significant worsening of pre-existing conditions.
- Reasons for admission to hospital or surgical procedures unless these were planned before the subject consented to trial participation.
- AEs commonly observed, and AEs anticipated based on the pharmacological effect of the IMP.
- Any laboratory abnormality assessed as clinically significant by the investigator (see Section 11.4.4).

Serious adverse event definition

An SAE is any untoward medical occurrence that

- Results in death.
- Is life-threatening.

- Requires inpatient hospitalisation or prolongation of existing hospitalisation. Planned hospitalisation or planned prolonged hospitalisation do not fulfil the criteria for being an SAE but should be documented in the subject's medical record.
- Results in persistent or significant disability/incapacity.
- Is a congenital anomaly/birth defect.

or

- Is a medically important condition. Events that may not be immediately life-threatening or result in death or hospitalisation but may jeopardise the subject or may require intervention to prevent one of the other outcomes listed in the definition above. Examples are intensive treatment in an emergency room or at home for allergic broncospasm, blood dyscrasias and convulsions that do not result in hospitalisation, development of drug dependency or drug abuse.

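### Section 11.4.5 and Appendix 1 conflict on whether non-serious stinging or burning that ends treatment is an AE, so such stops may be missing from the AE-leading-to-discontinuation tables

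*Combined protocol and SAP*

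**What the plan says.** Section 11.4.5 has the investigator ask each subject about stinging/burning in connection with IMP applications since the last visit, graded 0 to 3. On reporting it says: "Local tolerability reactions are not reported as AEs; however, if they qualify as an SAE, they will be reported" under Section 13.4.1. Seriousness is the only exception, so a non-serious grade 3 reaction is also exempt.

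The general AE rules contain no matching exemption:

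- Appendix 1, on exposure to a product: "An AE can therefore be any unfavourable and unintended sign (including an abnormal laboratory finding), symptom, or disease temporally associated with the use". Its list of inclusions also takes in whatever prompts an unwanted, unscheduled alteration of a drug or its dose.
- Section 10.2.1: the stopping reason under which intolerance would fall begins "An AE that, in the opinion of the investigator".
- Section 13.3: "any action taken with IMP as a consequence of the AE must be recorded (dose not changed, drug withdrawn, not applicable, unknown"). A companion field records whether the AE led to withdrawal from the trial.
- Section 10.1: the listed reasons for stopping include adverse event and other. For either, "a specification must be provided in the eCRF with a clear link to the specific AE if applicable".

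The planned outputs are:

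- Section 14.3.1: "The reasons for permanent discontinuation of IMP and withdrawal from trial will be presented for all randomised subjects by treatment group".
- Section 14.3.9.1: "AEs leading to withdrawal from trial and AEs leading to permanent discontinuation of IMP will be tabulated by treatment group", and an overall summary in which "premature discontinuations from the trial due to AEs, treatment-related AEs and severe AEs will be presented".
- Section 14.3.9.4: tolerability grades summarised by visit and treatment group.

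**The concern.** In a dose-ranging trial of a topical product, stopping because the cream burns is the most consequential tolerability outcome, and a reader would look for it in the table of AEs that ended treatment. Under 11.4.5 a non-serious case generates no AE record, and that table is built from AE records. Under Appendix 1 the same case does generate one. With about 25 sites and no stated precedence, the table could reflect how a site read the protocol as well as what happened to its subjects.

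At stake is the descriptive comparison of four strengths with vehicle on the listed safety endpoint, the number of AEs (Section 6, under other endpoints). Section 5.3 says the results will support phase 3 dose selection, although the method named to guide that choice (Section 14.3.5) is dose-response modelling of efficacy.

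**Working it through.** The protocol states no figure on this point, so the check is mainly textual. Take one case: a subject has non-serious burning on application and permanently stops IMP because of it.

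**Path A, the site follows 11.4.5.**
1. There is no AE record, because the reaction is not serious.
2. The action-taken and withdrawn-due-to-AE fields in 13.3 belong to an AE, so there is nowhere to enter them.
3. The case is absent from the AE counts and from the table of AEs leading to IMP discontinuation or withdrawal. If the subject also leaves the trial, it is absent from the overall-summary line on premature discontinuations due to AEs.

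**Path B, the site follows Appendix 1.**
1. The burning is the reason for an unplanned change in medication, hence an AE.
2. Section 13.3 then records that the drug was withdrawn.
3. The case appears in all the outputs that apply to it.

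**Which path applies?** Neither section refers to the other. Section 13.2 points to Sections 11.4.1 to 11.4.4 for eCRF entry principles and does not mention 11.4.5. One may argue that the specific rule governs, or that the wording of 10.2.1 already makes such a reaction an AE. The documents do not settle it.

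**What survives on Path A?**
- The reason for stopping, on the end of trial form. If 'other' is chosen a specification is mandatory (10.1), and reasons are presented by arm (14.3.1).
- The worst grade since the last visit, due at the early termination visit (Section 4, Panel 2 and footnote 3; 11.4.5).
- Burning that is a worsening of the eczema, which has its own AE route in 13.6.6.

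No output described in Section 14 joins the stop reason to the tolerability grade, and narratives are specified for SAEs only.

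**Scale.** Input: 50 subjects per arm (Sections 7.2 and 14.1). Each omitted stop is 1/50 = 2 percentage points. The safety set drops subjects who never used IMP, so the actual denominator may be slightly smaller.

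The frequency r of burning-related stops is not given, so the rates below are assumptions. Expected number per arm = 50r; chance of at least one in an arm = 1 − (1 − r)^50.

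| Assumed r | Expected per arm | Chance of at least one in an arm | Expected in 200 active subjects |
|---|---|---|---|
| 1% | 0.5 | 39% | 2 |
| 2% | 1.0 | 64% | 4 |
| 5% | 2.5 | 92% | 10 |
| 10% | 5.0 | 99% | 20 |

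These are numbers of stops. How many would be omitted depends on how many sites take Path A; the table is the ceiling, with all of them doing so.

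**The case against.** The strongest reply is that Appendix 1 already answers the question: a reason for an unplanned medication change is an AE, and an investigator who stops IMP because a reaction contraindicates further dosing has, by 10.2.1, already judged it an AE. On that view nothing is lost. Keeping solicited tolerability grades apart from spontaneous AEs is also a legitimate design choice with its own by-arm summary. And the residue is small: visible reactions or a diagnosis at treated skin remain AEs under 13.3, and worsening eczema does under 13.6.6.

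Much of this stands. It rules out several stronger readings that a reader might infer:

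- *That burning-related stops are bound to be missing from the AE tables.* This needs 11.4.5 to override Appendix 1, which no text says.
- *That the stop would be untraceable.* The disposition reason, with a mandatory specification under 'other', and the early-termination grade both remain.
- *That the disposition and AE tables must disagree.* This happens only if a site codes the stop as an adverse event yet records no AE. Section 10.1 asks for the link only if applicable, so a missing link is not itself a breach.
- *That observed-cases tabulation (14.3.12) hides the reaction.* The scale concerns applications since the last visit, and IMP may not be restarted, so later visits have no further applications to grade.

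What the objection does not do is remove the conflict. Section 11.4.5 states a flat exemption with one exception, and a site applying it literally would be following the protocol.

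**Conclusion.** The point holds as an unresolved conflict between passages, not as a certain loss of data. Depending on which passage a site follows, a non-serious, sensory reaction to application that ends treatment is either in or out of the AE counts and the AE-leading-to-discontinuation tables, and the protocol describes no other output that shows such stops by arm.

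The size is 2 percentage points of an arm per omitted stop. The number of stops cannot be derived from the documents, and the rates tabulated above are illustrations. No test or confidence interval is described for AEs, so the consequence is a less reliable descriptive table rather than a wrong inference. The primary and secondary efficacy analyses do not depend on AE coding and are unaffected.

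The conclusion rests on the text of the protocol. Section 14.3.12 leaves room for the statistical analysis plan to be finalised before unblinding, and a linking listing could be specified there, though that would not settle what sites record. This is a cheap improvement.

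**What to change.** Reconcile the passages. The change concerns recording only and leaves the rules for stopping IMP and all other clinical management as they are.

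1. In 11.4.5, add: 'A local tolerability reaction leading to permanent discontinuation of IMP or withdrawal from the trial is also recorded as an AE.'
2. In 10.1, state that the reason for such a stop is coded as adverse event and linked to that AE.
3. If Appendix 1 or 13.3 is aligned as well, use only a cross-reference to 11.4.5, limited to non-serious stinging/burning in connection with IMP application that does not lead to such a stop. A broader exemption would cut across 13.6.6, because burning is also an eczema symptom in the HESD. Leave 13.6.6 unchanged.

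Cost: one sentence in 11.4.5, a coding note in 10.1, an optional cross-reference, and eCRF guidance to sites. No new eCRF field is needed, because 13.3 already has both the action-taken and the withdrawal fields. The downside is a slightly higher AE count. The exemption for all other solicited, non-serious reactions stays in place.
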